- The pre-dose average concentration for single-dose data from non-endogenous compounds will be set to zero. Otherwise, only quantifiable concentrations will be used to calculate average concentrations.
- Concentrations at a sampling time exceeding the sampling time window specified in the protocol, or $\pm 10\%$, will be excluded from the average concentration profiles.
- Concentrations excluded from the mean calculation will be documented in the final study report.
- A concentration average will be plotted for a given sampling time only if 2/3 of the individual data at the time point have quantifiable measurements that are within the sampling time window specified in the protocol or $\pm 10\%$. An average concentration estimated with less than 2/3 but more than 3 data points may be displayed on the mean concentration plot if determined to be appropriate and will be documented within the final study report.

Treatment of Outliers during Pharmacokinetic Analysis

Application of this procedure to all PK analyses is not a requirement. Rather, this procedure provides justification for exclusion of data when scientifically appropriate. This procedure describes the methodology for identifying an individual value as an outlier for potential exclusion, but does not require that the value be excluded from analysis. The following methodology will not be used to exclude complete profiles from analysis.

Data within an Individual Profile

A value within an individual profile may be excluded from analysis if any of the following criteria are met:

- For PK profiles during single dosing of non-endogenous compounds, the concentration in a pre-dose sample is quantifiable.
- For any questionable datum that does not satisfy the above criteria, the profile will be evaluated and results reported with and without the suspected datum.

Data between Individual Profiles

1. If $n < 6$, then the dataset is too small to conduct a reliable range test. Data will be analyzed with and without the atypical value, and both sets of results will be reported.
2. If $n \geq 6$, then an objective outlier test will be used to compare the atypical value to other values included in that calculation:
 - a. Transform all values in the calculation to the logarithmic domain.
 - b. Find the most extreme value from the arithmetic mean of the log transformed values and exclude that value from the dataset.

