 - c. Calculate the lower and upper bounds of the range defined by the arithmetic mean $\pm 3 \times \text{SD}$ of the remaining log-transformed values.
 - d. If the extreme value is within the range of arithmetic mean $\pm 3 \times \text{SD}$, then it is not an outlier and will be retained in the dataset.
 - e. If the extreme value is outside the range of arithmetic mean $\pm 3 \times \text{SD}$, then it is an outlier and will be excluded from analysis.

If the remaining dataset contains another atypical datum suspected to be an outlier and $n \geq 6$ following the exclusion, then repeat step 2 above. This evaluation may be repeated as many times as necessary, excluding only one suspected outlier in each iteration, until all data remaining in the dataset fall within the range of arithmetic mean $\pm 3 \times \text{SD}$ of the log-transformed values.

Reporting of Excluded Values

Individual values excluded as outliers will be documented in the final report. Approval of the final report will connote approval of the exclusion.

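### SAP 9.3 contradicts itself on whether a PK value that fails the 3-SD outlier test must be excluded, and at n=6 or more it does not ask for results both with and without that value

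*SAP*

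**What the plan says.** SAP 9.3, under the heading on treatment of outliers, opens permissively. It states: "Application of this procedure to all PK analyses is not a requirement". It adds: "Rather, this procedure provides justification for exclusion of data when scientifically appropriate". It describes itself as a method for "identifying an individual value as an outlier for potential exclusion, but does not require that the value be excluded from analysis".

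The between-profile rules then depend on n.

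- **n below 6:** the SAP regards the dataset as too small for a reliable range test and says: "Data will be analyzed with and without the atypical value, and both sets of results will be reported".
- **n of 6 or more:** "then an objective outlier test will be used to compare the atypical value to other values included in that calculation". On the log scale, the most extreme value is set aside and compared with the mean ± 3 SD of the rest. Step 2d retains a value inside the range. Step 2e says that if it lies outside, "then it is an outlier and will be excluded from analysis".

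Within a single profile, for any questionable datum other than a quantifiable pre-dose concentration, "the profile will be evaluated and results reported with and without the suspected datum". On reporting, "Individual values excluded as outliers will be documented in the final report". The SAP gives no cut-off for an atypical value and no error rate for the test.

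**The concern.** There are two gaps in the text. First, the opening paragraph leaves exclusion to judgement while step 2e makes it automatic. Two analysts following the same SAP could treat the same flagged value differently. Second, both-ways reporting is the rule within a profile and for small between-profile datasets, but it stops at n=6. That is the planned active group size, and no reason is given for stopping there.

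At stake are the cohort-level geometric mean, geometric CV% and 90% CI for LY3478045 exposure. If a valid value is removed and only the reduced result is tabulated, between-subject variability in this first-in-human study looks smaller than it is. How much this matters depends on how often the test labels a valid value as an outlier at n=6.

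**Working it through.** **Inputs**

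- Six subjects receive LY3478045 in each Part A cohort (SAP 5.1) and each Part B cohort (SAP 5.2). Placebo samples are not assayed for LY3478045 (Protocol 9.5.1), so n=6 is the planned size of a cohort-level calculation.
- Test: the most extreme log value against the mean ± 3 SD of the other five (SAP 9.3, steps 2a to 2e).
- Assumption: valid values are log-normal. The SAP treats AUC and Cmax this way in 9.1.
- Assumption: because the SAP does not define atypical, the trigger for testing is varied. Only a most-extreme value beyond 2, 2.5 or 3 true SDs from the true mean is tested.

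The documents state no error rate, so there is no figure of theirs to reproduce.

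**Step 1: ceiling, if every clean cohort were tested.** For a given value x, with mean m and SD s of the other five, (x − m)/(s·√(1 + 1/5)) follows a t distribution with 4 df. The 3-SD limit is therefore |t| > 3/√1.2 = 2.739, with probability 0.0520. Over six values, 6 × 0.0520 = 0.312. Simulation of 2,000,000 clean cohorts also gives 0.312. By the same formula the rate is 27% at n=7 and 25% at n=8.

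**Step 2: testing only values that look extreme** (simulation, n=6, all values valid).

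| Trigger (true SDs) | Cohorts with such a value | Labelled outlier, if tested | Cohorts with a false label |
|---|---|---|---|
| 2 | 20.5% | 49% | 0.205 × 0.49 ≈ 10% |
| 2.5 | 6.5% | 59% | 0.065 × 0.59 ≈ 4% |
| 3 | 1.5% | 71% | 0.015 × 0.71 ≈ 1% |

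These rates are per cohort and per parameter.

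**Step 3: effect of one deletion.** Among cohorts falsely flagged with the 2-SD trigger, the mean log-SD goes from 1.24 to 0.64 of its true value, a ratio of 0.64/1.24 = 0.52. The log mean moves by about 0.44 SD, up or down. With an assumed CV of 30%, the log-SD is √ln(1.09) = 0.294 and the geometric mean moves by about −12% or +14%. With an assumed CV of 50%, the log-SD is √ln(1.25) = 0.472 and the move is about −19% or +23%. The signed shift averages zero, so log exposure has no average bias.

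**Step 4: detection of real errors.** With one of six values shifted by 2, 3, 4, 5 or 6 SD, the test correctly flags it in 30%, 56%, 79%, 92% or 98% of cohorts.

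**Step 5: dose proportionality.** The power model was simulated with 6 subjects per dose, 4 or 5 doses equally log-spaced from 20 to 320 mg, and flagged values deleted by cohort. Coverage of the 90% CI for the slope is about 88.5%, 89.6% and 90% for the 2, 2.5 and 3-SD triggers, against 90% with no deletion. The SAP does not say whether a cohort-level deletion carries into this model.

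**The case against.** The strongest reply is that the opening paragraph governs the whole procedure. It decides whether the test is invoked and whether exclusion follows, exclusion is tied to scientific appropriateness, and steps 2c to 2e are only the mechanics. This is a natural reading and may be the intended one. The SAP does not say so, however, and step 2e is categorical, so the wording still needs reconciling.

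Several safeguards also stand:

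- The method may not be used to remove whole profiles.
- A repeat needs at least six remaining values, so at n=6 at most one value per calculation can go.
- If a subject's value is missing and n falls to 5, both-ways reporting returns.
- All databased data are listed (SAP 9.1) and exclusions are documented, so a reader can recompute the result.

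A reader might infer that 31% of cohorts will lose a valid value. The documents do not support that. The figure requires the test to be run on every clean cohort, whereas the SAP makes use optional and starts from a value already thought atypical. It is an upper bound. A reader might also infer that the test cannot separate bad data from good. Detection of 92% at 5 SD and 98% at 6 SD shows otherwise. The weakness is that it too easily confirms valid extremes.

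**Conclusion.** The contradiction and the reporting gap are in the text and need no simulation. The size of the consequence rests on log-normality and on assumed triggers: about 10%, 4% or 1% of cohorts per parameter with a valid value labelled an outlier, and roughly half the log-SD lost in a cohort where that value is deleted.

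The harm is limited. LY3478045 PK is the secondary objective and the remaining PK and PD objectives are exploratory (SAP 4.2 and 4.3), so the primary safety objective is untouched. Average log exposure is not biased. It would be wrong to conclude that the dose-proportionality intervals are seriously too narrow, since coverage stays between about 88.5% and 90% under the SD triggers. This is a minor point and a cheap improvement.

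**What to change.** 1. Reword step 2e to agree with the opening paragraph, for example: *the value is flagged as a potential outlier and may be excluded when scientifically appropriate, with the reason documented*.
2. Extend the SAP's own rule for n below 6, so that between-profile results with and without any flagged value are reported at every n.

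Keep the 3-SD test as the flag. A limit of about 5.3 SD would hold the clean-cohort rate at 5% for n=6, but it would cut detection of a 6-SD error from 98% to 70%. It is not recommended, because both-ways reporting deals with the problem without that loss.

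The cost is two wording changes and a little more reporting. Design and data collection do not change.

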9.3.1 Pharmacokinetic Statistical Methodology

All PK parameters will be summarized using descriptive statistics.

PK dose proportionality will be assessed separately for Parts A and B (on Day 14 for Part B). Log-transformed C_{max} , AUC_{T} (Part B only), and $AUC(0-\infty)$ of LY3478045 will be evaluated using a power model (where log-dose acts as an explanatory variable) to estimate ratios of dose-normalized geometric means and corresponding 90% confidence intervals (CIs). The estimated ratio of dose-normalized geometric means of PK parameters between the highest and lowest doses will be used to assess dose proportionality. A subinterval within the highest and lowest doses may also be considered for assessment of dose proportionality using the same approach. The dose proportionality analysis for Part B will only be conducted if there are at least 3 different LY3478045 dose levels available for analysis.

Examples of the SAS code that will be used are as follows:

```
proc mixed data=xxxx;
model log_pk = log_dose / alpha=0.1 cl solution outpred=resids ddfm=kr;
estimate 'xx mg' intercept 1 log_dose yy / alpha=0.1 cl; /*Log value of xx*/
estimate 'zz mg - xx mg' log_dose pp / alpha=0.1 cl; /*Difference in log
values of zz and xx*/
ods output solutionf=est;
ods output estimates=estims;
run;
```

In Part B, the PK parameters, AUC_{T} , $AUC(0-\infty)$, and C_{max} , will be log-transformed prior to analysis. A linear mixed effects model will be fitted to the data. The model will include Subject as a random effect, and Day as a fixed effect. For each PK parameter, the difference in least-square treatment means (Day 14 – Day 1) along with the 90% CIs will be back-transformed to produce the ratio of geometric means and the CIs comparing Day 14 to Day 1.

Example of SAS code as follows:

```
proc mixed data=xxxx;
by treatment;
class day subject;
model log_pk = day /residual ddfm=kr;
random subject;
lsmeans day / cl pdiff alpha=0.1;
ods output lsmeans=lsm diffs=estims;
run;
```

To assess the effect that LY3478045 has on the primary **CCI** PK parameters, $AUC(0-\infty)$ and C_{max} , a linear fixed effect model on the parameters will be used. The response of the model will be the logged ratio of observations on Day 7 to Day-2. The model will include Treatment and the log of the baseline (Day -2) observation as fixed effects. For the Day 7 observations in Cohorts 2 and 4, the difference in least-square treatment means ([LY3478045 + **CCI**] –

[Placebo + CCI █] along with the 90% CIs will be back-transformed to produce the ratio of geometric means and the CIs comparing (LY3478045 + CCI █) to (Placebo + CCI █).

Example of SAS code as follows:

```
proc mixed data=xxxx;
  class treatment baseline;
  model log_ratioPK = treatment log_baseline / residual ddfm=kr;
  lsmeans treatment / cl pdiff alpha=0.1;
  ods output lsmeans=lsmeans diffs=estims;
  run;
```

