5.4. Scientific Rationale for Study Design

Healthy Subjects

Conducting the study in healthy subjects mitigates the potential confounding effects of the disease state and concomitant medications in patients, and therefore provides the most unbiased assessment of the safety and tolerability in this first-in-human study.

Sentinel Dosing

Consistent with the concept of sentinel dosing (EMA 2017), sentinel dosing will be performed in:

Part A: Cohorts 3, 4, and 5 as the exposures of LY3478045 in these cohorts may approach 1/10th the exposure at the NOAEL (CCI ██████████). Sentinel dosing will not be performed in Cohorts 1 and 2 as LY3478045 exposures in these cohorts are anticipated to be substantially below 1/10th the exposure at the NOAEL.

Part B: Sentinel dosing will be included for the cohort(s) of female subjects tested at dose(s) predicted to result in mean exposure(s) between **CCI**

Blinding

A subject- and investigator-blinded, randomized, placebo-controlled design has been chosen to minimize bias during the conduct of the study.

Clinical Data

Safety, tolerability, PK, and PD data in healthy subjects will assist in identifying an appropriate dose range for subsequent clinical studies.

Periodic Reviews

Periodic trial-level safety data reviews will ensure that any subject can be discontinued early, or the dose escalation can be terminated, or the study can be terminated, in case of any AE requiring such a decision.

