Appendix 2 lists the laboratory tests that will be performed for this study.

Appendix 5 provides a summary of the maximum number and volume of invasive samples, for all sampling, during the study.

Unless otherwise stated in the subsequent subsections, all samples collected for specified laboratory tests will be destroyed within 60 days of receipt of confirmed test results. Certain samples may be retained for a longer period, if necessary, to comply with applicable laws, regulations, or laboratory certification standards.

The specifications in this protocol for the timings of safety, PK, and PD sampling are given as targets to be achieved within reasonable limits. Modifications may be made to the time points based upon the safety and PK information obtained. The scheduled time points may be subject to minor alterations; however, the actual time must be correctly recorded in the electronic case report form (eCRF). Failure to obtain samples due to clinical issues, such as problems with venous access, technical difficulty with obtaining samples, or if the subject does not show up for planned procedural visits will not be considered a protocol deviation. However, the CRU will still be required to notify the sponsor in writing to account for missing samples to facilitate data reconciliation.

If the predicted mean exposure for the dose at any cohort is estimated to be higher than 71.7 $\mu\text{g}\cdot\text{hr}/\text{mL}$, only female subjects will be included in the cohort and mandated to stay in the CRU until 24 hours after the last dose.

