5.2 Part B

[figure not shown]
Part B will be initiated after assessing safety, tolerability, PK, and PD data through Cohort 3 in Part A.

Multiple-ascending oral doses of LY3478045 will be administered once daily (QD) for 14 days in up to 4 cohorts. Each cohort will consist of 8 subjects. In Cohorts 1 and 3, six subjects will receive LY3478045 and 2 subjects will receive placebo. In Cohorts 2 and 4, six subjects will receive LY3478045 co-administered with a single dose of [CC1] and 2 subjects will receive placebo with a single dose of [CC1]. The maximum dose in males and females will be determined based on the PK analyses from previous cohorts.

A sentinel dosing strategy will be utilized in Cohorts 3 and 4, for which the mean AUC(0-24) is predicted to exceed [CC1] $\mu\text{g}\cdot\text{hr}/\text{mL}$. Two subjects (1 LY3478045 and 1 placebo) in the cohorts for which the mean AUC0-24 is predicted to exceed [CC1] $\mu\text{g}\cdot\text{hr}/\text{mL}$ will receive a sentinel dose on the same day. At least 48 hours after dose, the remaining subjects in each cohort may be dosed based on the available safety data.

Male subjects are allowed in Part B in the cohorts for which the predicted mean exposure AUC0-24 levels for the dose will not exceed [CC1] $\mu\text{g}\cdot\text{hr}/\text{mL}$, 1/10th exposure level observed at [CC1] mg/kg in dogs, which is the lowest dose tested in dogs with no testicular findings, as determined from PK data in Parts A and B.

Female subjects are allowed in Part B in every cohort. The predicted mean exposure AUC0-24 levels for the doses investigated in Part B will not exceed [CC1] $\mu\text{g}\cdot\text{hr}/\text{mL}$, 1/12th exposure level observed at [CC1] mg/kg in dogs, as determined from PK data in Parts A and B.

Abbreviations: AT = atorvastatin; LY = LY3478045; PL = placebo.

Figure GZKA.2 Illustration of study design for Part B

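### Part B dose proportionality: if the upper cohorts are women-only and the lower ones include men, a log-dose-only model cannot separate dose from sex

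*SAP*

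**What the plan says.** **Model.** SAP Section 9.3.1 assesses proportionality separately for Part A and for Part B (Day 14). The code has one explanatory variable: "model log_pk = log_dose / alpha=0.1 cl solution outpred=resids ddfm=kr". The reading is then fixed: "The estimated ratio of dose-normalized geometric means of PK parameters between the highest and lowest doses will be used to assess dose proportionality". A 90% confidence interval is given, but no null hypothesis and no acceptance limit. The Part B assessment will "only be conducted if there are at least 3 different LY3478045 dose levels available for analysis". A narrower dose range may also be examined; that option is discretionary and not linked to sex.

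**Who receives which dose.** Footnote e to both Part B schedules, repeated at the start of Protocol Section 9, applies when a cohort's predicted mean exposure is above 71.7 µg·hr/mL: "only female subjects will be included in the cohort and mandated to stay in the CRU until 24 hours after the last dose". Protocol Section 7.4.1 admits men to Part B only below an exposure limit and women to every cohort. For Part A it sets one limit for both sexes.

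**What the sponsor seems to expect.** Protocol Section 5.4 on Part B: "Sentinel dosing will be included for the cohort(s) of female subjects tested at dose(s) predicted to result in mean exposure(s) between" two redacted limits. SAP Section 5.2: "A sentinel dosing strategy will be utilized in Cohorts 3 and 4, for which the mean AUC(0-24) is predicted to exceed" a redacted value. SAP Section 9.6.9 flags out-of-range testicular hormone values in Part B Cohorts 1 and 2 only.

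**Use of sex.** Sex is summarized as a demographic variable (SAP Section 9.2). It appears in no PK model, and Protocol Section 7.2 states no stratification by sex.

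**The concern.** A power model with log-dose alone attributes every systematic difference between low-dose and high-dose subjects to dose. In Part B an eligibility rule, not chance, may make the high-dose subjects all women while the low-dose subjects are mixed. The highest-to-lowest ratio would then estimate non-proportionality multiplied by part of any sex difference in exposure.

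The error can go either way. Proportional PK can look more or less than proportional, and real non-proportionality can be partly cancelled. PK is the secondary objective, and the Day 14 result is the repeat-dose statement on proportionality in a study meant to inform the dose range for patient studies. The primary safety objective is not touched.

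**Working it through.** The plan gives no power, precision target or acceptance limit for proportionality, so there is no figure to reproduce.

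**Inputs from the documents.** Up to 4 Part B cohorts with 6 active subjects each, so 24 active; log-dose as the only term; the women-only rule.

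**Assumed, because the documents do not give them.** Four equally log-spaced doses; Cohorts 3 and 4 all women; a share p of women in Cohorts 1 and 2; the female-to-male exposure ratio F/M at equal dose. For power and interval width only: between-subject CV 30% and doubling doses (8-fold range).

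**Bias.** Code log-dose as −1.5, −0.5, 0.5, 1.5 and the share of women as p, p, 1, 1.

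- Covariance of sex and dose: (−1.5p − 0.5p + 0.5 + 1.5)/4 = 0.5(1−p).
- Variance of dose: (2.25 + 0.25 + 0.25 + 2.25)/4 = 1.25.
- Slope bias per dose step: ln(F/M) × 0.5(1−p)/1.25 = 0.4(1−p) ln(F/M).
- Highest to lowest is three steps, so the ratio is multiplied by (F/M)^(1.2(1−p)), whatever the common spacing.
- If only the top cohort is all women: covariance 1.5(1−p)/4 = 0.375(1−p), giving an exponent of 3 × 0.375(1−p)/1.25 = 0.9(1−p).

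For p = 1/3 and the top two cohorts all women, the exponent is 1.2 × 2/3 = 0.8:

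| F/M | fitted ratio when the true ratio is 1 |
|---|---|
| 0.8 | 0.84 |
| 1.0 | 1.00 |
| 1.15 | 1.12 |
| 1.25 | 1.19 |
| 1.4 | 1.31 |
| 1.5 | 1.38 |

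Masking: a true ratio of 0.80 with F/M = 1.25 is estimated at about 0.80 × 1.195 = 0.96.

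At p = 1 (no men in the lower cohorts) the exponent is 0 and there is no bias.

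**Cost of a sex term.** The slope standard error rises by 1/√(1−R²), where R² is the squared correlation of sex and log-dose. The variance of sex is m(1−m), with m = (1+p)/2.

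- p = 1/2: R² = 0.25²/(1.25 × 0.1875) = 0.267; factor 1.17.
- p = 1/3: R² = 0.333²/(1.25 × 0.222) = 0.40; factor 1.29.
- p = 0: R² = 0.5²/(1.25 × 0.25) = 0.80; factor 2.24.

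Simulation (20,000 trials per setting) confirmed that both the sex-term fit and the women-only fit centre on 1.00 when PK is proportional. The multiplicative half-width of the 90% interval was:

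| Women in each lower cohort | planned fit (no sex effect) | with sex term | women only |
|---|---|---|---|
| 3 of 6 | 1.31 | 1.38 | 1.40 |
| 1 of 6 | 1.31 | 1.52 | 1.61 |
| 0 of 6 | 1.31 | 1.84 | 2.46 |

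With p = 1/3, a true exponent of 0.85 and no sex effect, the chance that the 90% interval excludes 1 falls from about 59% (planned fit) to 43% (with a sex term).

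**The case against.** The women-only rule is conditional. Part B doses are chosen from emerging PK, there may be fewer than four cohorts, and the sentinel limits are redacted, so neither can be matched to 71.7 µg·hr/mL. This stands: a women-only Cohort 3 and Cohort 4 is an inference from three places in the documents, not a stated fact.

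No passage says that LY3478045 exposure differs by sex. This also stands: only the mechanism is established, and every size above depends on an assumed F/M.

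A reader might infer that the plan's proportionality test has an inflated error rate. Under the assumptions above with p = 1/3, the 90% interval excludes 1 in about 17% to 54% of trials for F/M of 1.15 to 1.5 when PK is proportional. The documents do not support that reading. The SAP names no null and no acceptance limit, and Protocol Section 10.3.2.2 says only that the power parameter is evaluated. What can be shown is a shifted ratio and interval, not a stated test going wrong.

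The consequence is limited. Part A assesses proportionality separately and is unaffected, and dose escalation rests on safety and predicted exposure, not on this interval. But Part A is single-dose and cannot replace the Day 14 assessment. SAP Section 3 permits supplementary analyses, but these would be chosen after the data are seen.

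Finally, with 24 active subjects, adjustment is expensive when sex and dose nearly coincide. That is a sound reason not to replace the planned model; it does not justify leaving the overlap unexamined.

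**Conclusion.** The point holds conditionally. If at least one Part B cohort is women-only, the lower cohorts include men, and exposure at equal dose differs by sex, the Section 9.3.1 ratio is biased by a factor that follows from the design. With the top two of four equally spaced cohorts all women, that factor is (F/M)^(1.2(1−p)): 1.12 to 1.38 for an assumed F/M of 1.15 to 1.5 and p = 1/3, and below 1 if women have the lower exposure. It is exactly 1 if F/M is 1, if no cohort passes the limit, or if the lower cohorts have no men.

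The documents do not establish that the top doses will certainly go only to women, that a sex difference exists, or that a sex-adjusted model is the better single basis for the conclusion. The weakness is that the plan has no provision for a confounding that its own eligibility rule can create. It concerns a secondary objective, in Part B only.

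**What to change.** In SAP Section 9.3.1, for Part B:

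- Keep the planned log-dose fit.
- Pre-specify beside it (a) the same power model with sex as a fixed effect and (b) a fit in women only, each with the highest-to-lowest dose-normalized ratio and 90% confidence interval.
- Report the number of men and women at each dose.
- State in advance that if any cohort is women-only and the fits disagree, or too few women are in the lower cohorts to separate sex from dose, the CSR will say that the Part B ratio cannot be attributed to dose alone and will read it with Part A.

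Restricting the claim to doses given to both sexes is not a safe fallback. If only Cohorts 1 and 2 are mixed, two dose levels remain, below the SAP's minimum of three. The optional narrower range does not help either if it reuses the slope fitted to all cohorts.

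The cost is SAP wording and two extra fits on data already collected. The adjusted fit is less precise: the slope standard error is about 17% larger with half women in the lower cohorts, 29% with one third and 124% with none. With none, the women-only fit would also rest on two dose levels. For this reason the extra fits belong alongside the planned one and should not replace it.

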5.5. Justification for Dose

A planned dose range of 20 to 320 mg was selected to assess safety, tolerability, PK, and PD of LY3478045 following SAD and MAD in healthy subjects:

The planned starting dose in Part A (SAD) is 20 mg in both male and female subjects. The planned top dose in Part A (SAD) is a dose that is predicted to not exceed the mean exposure **CCI** (it is currently anticipated that this dose is 320 mg; however, the exact dose will be determined once PK data are analyzed from the previous cohorts in Part A).

The human PK in healthy subjects was projected with physiologically based pharmacokinetic (PBPK) modeling using data from in vitro studies in human systems. **CCI**

The predicted efficacious dose is 100 to 200 mg once daily based on maintaining plasma exposure over the total cell-based KHK half maximal inhibitory concentration for 24 hours. The PD measurement of serum fructose in Part A (SAD) will define the level of target engagement at each dose, which will further allow refinement of predicted efficacious dose.

The starting dose of **CCI**

[REDACTED]

The dose levels in MAD (Part B) will be selected based on available PK/PD data from Part A. The maximum dose in males in the MAD will be determined based on the PK analyses from previous cohorts to ensure that the predicted mean exposure AUC0-24 at the maximum dose in males does not **CCI**. This is 1/10th of the mean exposure level observed at 75 mg/kg in dogs, which is the lowest dose tested in dogs with no testicular findings. The maximum dose in females in the MAD will be determined based on the PK analyses from previous cohorts to ensure that the predicted mean exposure AUC0-24 at the maximum dose in females does not exceed **CCI**. This is 1/12th of NOAEL exposure at **CCI** dose in dogs.

Table GZKA.2.

CCI

CCI

CCI

6. Study Population

Eligibility of subjects for the study will be based on the results of screening medical history, physical examination, vital signs, clinical laboratory tests, and ECG.

The nature of any conditions present at the time of the physical examination and any preexisting conditions will be documented.

Screening may occur up to 28 days prior to day of clinical research unit (CRU) admission. Subjects who are not enrolled within 28 days of screening may be subjected to an additional medical assessment and/or clinical measurements to confirm their eligibility.

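### The example dose-proportionality code in SAP 9.3.1 estimates the raw exposure ratio between two doses, whereas the text assesses the dose-normalized ratio

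*SAP*

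**What the plan says.** The dose-proportionality paragraph of SAP 9.3.1 says that log-transformed Cmax, AUC over the dosing interval (Part B only) and AUC to infinity will be "evaluated using a power model (where log-dose acts as an explanatory variable) to estimate ratios of dose-normalized geometric means", with 90% confidence intervals. It then names the deciding quantity: "The estimated ratio of dose-normalized geometric means of PK parameters between the highest and lowest doses will be used to assess dose proportionality". A subinterval of the dose range may be assessed in the same way.

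The example SAS code that follows has three relevant lines:

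- the model, "model log_pk = log_dose / alpha=0.1 cl solution outpred=resids ddfm=kr";
- an estimate at a single dose, "estimate 'xx mg' intercept 1 log_dose yy / alpha=0.1 cl; /*Log value of xx";
- the between-dose contrast, "estimate 'zz mg - xx mg' log_dose pp / alpha=0.1 cl", whose comment defines pp as the log of dose zz minus the log of dose xx.

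Protocol 10.3.2.2 is less specific. It calls for a power model and says that the power parameter will be evaluated.

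On doses, Protocol 5.5 says "A planned dose range of 20 to 320 mg was selected". It adds, for the top of Part A, "it is currently anticipated that this dose is 320 mg", with the exact dose to follow from earlier PK data. Part B dose levels are to be chosen from Part A data and are not given.

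**The concern.** The text and the code appear to describe two different quantities. A dose-normalized ratio equals 1 when exposure is proportional to dose. A raw exposure ratio equals the dose ratio in that case. If the contrast is exponentiated and reported under the text's label, the point estimate and interval will lie far from 1 for a proportional drug.

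Over a wide range the error would be conspicuous. Over a narrow subinterval, which the SAP allows, it might not be: the result could look plausible and point the wrong way. Characterising the PK is the study's secondary objective, and the protocol says that these data will help to identify the dose range for later studies.

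**Working it through.** The plan states no numerical result for this analysis, so there is no figure to reproduce. The check is algebra on the printed code, confirmed by a small simulation.

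**Algebra.** The power model is log(PK) = a + b × log(dose), where b is the slope.

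- Contrast in the code: pp × b, with pp = log(zz) − log(xx) = log(zz/xx).
- Back-transformed: exp(pp × b) = (zz/xx)^b, the raw ratio of geometric means.
- Quantity named in the text: [PK(zz)/zz] ÷ [PK(xx)/xx] = (zz/xx)^(b − 1) = exp(pp × b − pp).
- Difference on the log scale: exactly pp, whatever the value of b.

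**Numbers for the planned Part A range** (20 and 320 mg, Protocol 5.5). The dose ratio is 320/20 = 16 and pp = log(16) = 2.7726.

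| Slope b | Contrast pp × b | Back-transformed, 16^b | Quantity in the text, 16^(b − 1) |
|---|---|---|---|
| 0.8 | 2.218 | 9.19 | 0.574 |
| 0.9 | 2.495 | 12.13 | 0.758 |
| 1.0 | 2.773 | 16.00 | 1.000 |
| 1.1 | 3.050 | 21.11 | 1.320 |
| 1.2 | 3.327 | 27.86 | 1.741 |

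If the top dose were 160 or 240 mg (values assumed for illustration), exact proportionality would back-transform to 160/20 = 8 or 240/20 = 12.

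**Effect on the interval.** One simulated dataset used assumed doses of 20, 40, 80, 160 and 320 mg, six subjects per dose, true slope 1 and log-scale SD 0.3. The contrast as coded gave 14.57 (90% CI 11.43 to 18.58). Dividing all three values by 16 gives 0.911 (0.714 to 1.161), identical to refitting with log(PK/dose) as the response. The ratio of upper to lower limit is 1.63 both ways (18.58/11.43 and 1.161/0.714), so only the location moves.

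**A narrow subinterval.** Take a two-fold range and slope 0.8, both assumed. The code's contrast back-transforms to 2^0.8 = 1.74, which read as a dose-normalized ratio suggests more than proportional exposure. The quantity in the text is 2^(−0.2) = 0.87, which is less than proportional.

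**Is the response already divided by dose?** The code does not define `log_pk`. Three features of SAP 9.3.1 point to an undivided response: the paragraph describes the response simply as log-transformed Cmax and AUC; the first estimate line is labelled as the value at a given dose; and the next code block, comparing Day 14 with Day 1, reuses `log_pk` for parameters that are only log-transformed.

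**The case against.** The strongest reply is that the text is clear and the code is only an example. It has placeholders for doses and data, and it stops at log-scale output: at slope 1 over 20 to 320 mg the contrast line returns 2.77, not 16. Some post-processing is needed to obtain any ratio, and a programmer following the text could divide by the dose ratio there. The SAP also refers to a separate document of table shells, which might specify the step. This stands as far as it goes. A reader might infer that the study report will show 16 for a proportional drug; the documents do not support that, because the final step is not shown.

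A second reply is that `log_pk` could hold dose-normalized values, since SAP 9.3 says that dose-normalized AUC and Cmax will be calculated. AUC over the dosing interval is not in that list, but with once-daily dosing it corresponds to AUC(0-24), which is. So the list does not rule this reading out. The wording of the paragraph, the label of the first estimate and the reuse of the variable name still make it the less natural one.

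Third, the practical effect is bounded. The shift is a known constant that can be removed without refitting. The SAP sets no numerical acceptance limits for proportionality, so no prespecified pass or fail result reverses. A reader might also infer that dose escalation would be misled, but SAP 9.3 assigns those decisions to a separate interim PK analysis by the sponsor.

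What remains is that the one contrast printed for the deciding quantity estimates something else, and neither text nor code supplies the correction. Other analyses in the same section do state how their results are back-transformed.

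**Conclusion.** The mismatch is real, and the SAP should be corrected. With `log_pk` as log-transformed PK, the printed contrast estimates the raw ratio, and its point estimate and both 90% limits sit log(zz/xx) above those of the dose-normalized ratio. For a 20 to 320 mg range in Part A this is a factor of 16 after back-transformation. The factor holds only if 320 mg is the top dose given, and it does not carry over to Part B, whose doses are not stated.

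It would be too strong to call the power model itself wrong or the slope biased. The model, the slope, its standard error and the log-scale interval width are all unaffected. The model line already requests the slope with its 90% interval, and the code saves it. The fault lies in one contrast and the missing step after it.

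**What to change.** In SAP 9.3.1, state that pp = log(zz/xx) is subtracted from the estimate and from both confidence limits before back-transforming. Dividing the back-transformed ratio and limits by zz/xx is equivalent.

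Using log(PK/dose) as the response for this contrast also works, but the fitted slope then becomes b − 1, with proportionality at 0, and the single-dose estimate becomes a dose-normalized mean. The subtraction is therefore the simpler change. Whichever route is chosen, define `log_pk` explicitly.

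Add one sentence that the slope and its 90% CI will be reported, in line with Protocol 10.3.2.2. They are already in the output.

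The cost is a line of code and two or three sentences. No design, data collection or model refit is involved.
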